3.5.2 Secondary Efficacy Endpoints

For all key secondary endpoints measured on a continuous scale, a MMRM model described in section 3.5.1 will be used. Nominal p-value will be reported without correction for multiple comparisons.

Binary key secondary endpoints will be analyzed using Generalized Estimating Equations (GEE) with a binomial distribution, logit link function for odds ratios and identity link for risk differences, and unstructured covariance. In case of convergence issues, AR(1) covariance structure will be used. The model will include the categorical covariates of treatment group, visit, and visit by treatment group interaction term. Least squares means on the probability scale for each treatment arm with the corresponding 80% confidence intervals and odds ratios relative to the control arm will be computed.

Data transformation (e.g., logarithmic transformation) may be applied as appropriate. Other statistical models and additional analyses may also be performed as appropriate. Fisher's exact test may be used for binary endpoints in case GEE models do not converge.

In addition, the influence of baseline parameters on the primary endpoint will be evaluated as covariates in the linear model and in subgroup analysis as appropriate (see 4.4.5).

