4.2 STUDY POPULATION

4.2.1 Inclusion Criteria

Patients must meet the following criteria for study entry:

Ocular criteria for study eye:

- Macular edema associated with DR defined as macular thickening by spectral domain optical coherence tomography (SD-OCT) involving the center of the macula: CST of $\geq 325\mu\text{m}$ with Spectralis (Heidelberg) at screening (where Spectralis is not available, the following devices and CST thresholds are acceptable: CST $\geq 315\mu\text{m}$ for Cirrus, CST $\geq 315\mu\text{m}$ for Topcon, CST $\geq 295\mu\text{m}$ for Optovue)
- Decreased VA attributable primarily to DME, with BCVA letter score of 73–24 letters (inclusive) on ETDRS-like charts (20/40–20/320 Snellen equivalent) on Day 1
- Clear ocular media and adequate pupillary dilatation to allow acquisition of good quality retinal images to confirm diagnosis

General criteria:

- Diagnosis of diabetes mellitus (DM; Type 1 or Type 2), as defined by the World Health Organization and/or American Diabetes Association
- Able and willing to provide written informed consent and to comply with the study protocol according to International Conference on Harmonisation (ICH) and local regulations. Alternatively, a legally authorized representative must be able to consent for the patient according to ICH and local regulations.

RO6867461—F. Hoffmann-La Roche Ltd
34/Protocol BP30099, Version 3

- Age ≥ 18 years
- For women who are not postmenopausal (i.e. ≥ 12 months of non-therapy-induced amenorrhea, confirmed by FSH, if not on hormone replacement) or surgically sterile (absence of ovaries and/or uterus) agreement to remain abstinent or use combined contraceptive methods that result in a failure rate of $< 1\%$ per year during the treatment period and at least through 4 weeks after last dose.

Abstinence is only acceptable if it is in line with the preferred and usual lifestyle of the patient. Periodic abstinence (e.g., calendar, ovulation, symptothermal, or postovulation methods) and withdrawal are not acceptable methods of contraception.

Examples of contraceptive methods with an expected failure rate of $< 1\%$ per year include male sterilization, hormonal implants, proper use of combined oral or injected hormonal contraceptives, and certain intrauterine devices.

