6. STATISTICAL CONSIDERATIONS AND ANALYSIS PLAN

6.1 DETERMINATION OF SAMPLE SIZE

The sample size is based on the primary efficacy outcome of mean change in BCVA from baseline at Week 24 in the *treatment-naïve patients*. Each RO6867461 dose (Arms B and C) will be compared with the control group (Arm A).

Consider 50 *treatment-naïve* patients randomized to Arms A, B, and C, with a drop-out rate of 10%. Assuming a standard deviation of 11 letters, this sample size provides 80% power to detect a true difference of 5 letters at the one-sided α level of 10%. The minimum detectable difference is approximately 3 letters.

Approximately 60 previously IVT anti-VEGF treated patients will be enrolled in addition for exploratory analyses.

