2.1 RANDOMIZATION

After written informed consent has been obtained, all patients will receive a screening number assigned through the Interactive Voice and Web Response System (IxRS). After all patient eligibility requirements are confirmed on Day 1 visit the site personnel will contact the IxRS for assignment of a patient identification number (a separate number from the screening number).

Approximately 50 treatment-naïve patients will be randomized on each arm (1:1:1 randomization scheme) and approximately 30 patients previously treated with IVT anti-VEGF will be randomized into arms A and C. Randomization will be stratified for the three factors below:

- Baseline BCVA ETDRS letter score assessed on Day 1 (64 letters or better vs. 63 letters or worse)
- Previous Macular Laser treatment (Yes/No)

Previous IVT anti-VEGF treatment in study eye (Yes/No)

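### Analyse the binary secondary endpoints with a covariate-adjusted Week 24 model; the planned treatment-by-visit GEE omits the strata and baseline BCVA and has no settled rule for early cells without responders

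*SAP*

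**What the plan says.** SAP 1.2.3.2 defines every binary secondary endpoint at Week 24: gain of 15 letters or more, BCVA of at least 69 letters, BCVA of at least 84 letters, resolution of fluid, and resolution of macular leakage.

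SAP 3.5.2 analyses them by GEE with a binomial distribution and a "logit link function for odds ratios and identity link for risk differences, and unstructured covariance". On the terms it says: "The model will include the categorical covariates of treatment group, visit, and visit by treatment group interaction term". It asks for least squares means on the probability scale by arm, with 80% confidence intervals, and for odds ratios against the control arm. It does not list the visits that enter, name the visit to which the least squares means refer, or say how to treat a cell with no responders.

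The fallbacks run in order. AR(1) replaces the unstructured covariance if there are convergence problems. After that, Fisher's "exact test may be used for binary endpoints in case GEE models do not converge". The same section also allows other models as appropriate.

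Two other places matter. The primary model in SAP 3.5.1 includes the randomization stratification factors and continuous baseline BCVA; the binary model does not. Protocol 6.7.2 has Fisher's exact test as the planned method, with 95% rather than 80% intervals.

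**The concern.** The treatment-by-visit model has one free parameter per arm-by-visit cell. BCVA is measured from Day 7 (Protocol Appendix 1), and Protocol 4.2.1 caps entry at 73 letters. Reaching 84 letters therefore needs a gain of at least 84 − 73 = 11 letters, and few patients may have that in the first weeks. If no patient in an arm has responded at a visit, the logit for that cell has no finite value. Under the identity link the fitted risk is 0 and its variance is 0.

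The planned route for at least one named secondary endpoint could then depend on how the software treats a degenerate cell. The step after AR(1) is left to judgement once data are in hand. The model also gives up precision by ignoring strata and a baseline value that the trial already collects.

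**Working it through.** **Inputs from the documents.** About 50 treatment-naïve patients in each of three arms (SAP 2.1); entry BCVA 24 to 73 letters (Protocol 4.2.1); 10% drop-out and SD 11 letters (Protocol 6.1); BCVA at Day 7 and Weeks 4, 8, 12, 16, 20 and 24, so seven visits (Protocol Appendix 1).

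**The plan's own figure.** Protocol 6.1 states "80% power to detect a true difference of 5 letters at the one-sided α level of 10"%. With 50 × 0.9 = 45 per arm, the standard error is 11 × √(2/45) = 2.319. Power is Φ(5/2.319 − 1.282) = Φ(0.874) = 0.809. The minimum detectable difference is 1.282 × 2.319 = 2.97 letters. Both agree with the plan. It gives no figure for the binary endpoints.

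**Saturation.** Three arms by seven visits is 21 cells. The model has 1 + 2 + 6 + 12 = 21 parameters.

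**One visit.** With true responder rate p, the chance that at least one arm has 0 of 50 is 1 − [1 − (1 − p)^50]^3.

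| p | (1 − p)^50 | Chance of an empty arm |
|---|---|---|
| 0.5% | 0.778 | 99% |
| 1% | 0.605 | 94% |
| 2% | 0.364 | 74% |
| 3% | 0.218 | 52% |
| 5% | 0.077 | 21% |
| 10% | 0.005 | 1.5% |

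**All seven visits.** The rates by visit are not in the documents, so they are assumed: baseline mean 60 to 62, SD 10, truncated to 24–73; mean gain 2 to 6 letters at Day 7 and 8 to 13 at Week 24; SD of change 5 to 11 at Day 7 and 11 at Week 24. The chance of at least one empty cell, from 400 simulated trials per scenario, is:

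| Endpoint | Low gains | Middle | High | SD 11 at every visit |
|---|---|---|---|---|
| BCVA ≥ 84 | 99.8% | 94% | 36% | 18.5% |
| Gain ≥ 15 | 97% | 34% | 0.5% | 0% |
| BCVA ≥ 69 | 0% | 0% | 0% | 0% |

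**What the fits do.** The 84-letter endpoint was fitted under middle gains on complete data with a standard GEE routine (Python statsmodels):

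- Unstructured, logit link: 13 of 15 data sets converged, and 14 of 15 in a second set. Fitted logits in empty cells ran to about −33 to −36, which is where the iteration stopped and not an estimate.
- Unstructured, identity link: 7 of 15 converged.
- AR(1): 1 of 4 converged for each link in one set, but 15 of 15 with the identity link in another. The convergence flag is unstable. Changing the correlation does not alter an empty cell.
- The Week 24 contrast of Arm C with Arm A was finite in all 15 unstructured and all 4 AR(1) fits of the first set, for both links, and in nearly every fit overall. On complete data it equalled the plain Week 24 contrast.
- Every fit for gain ≥ 15 and BCVA ≥ 69 converged.

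**Least squares means.** If they were averaged over visits on the logit scale, one cell at −33 in place of logit(1%) = −4.6 would move the arm mean by 28.4/7 = 4.1 logits.

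**Value of adjustment.** In simulation, a Week 24 model with strata and baseline BCVA cut the variance of the risk difference, against the unadjusted contrast, by about 12% (≥ 84 letters) to 23% (≥ 69 letters). Since √0.88 = 0.94 and √0.77 = 0.88, intervals would be about 6% to 12% narrower.

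**The case against.** The endpoints are at Week 24. In a saturated model an empty Day 7 cell chiefly spoils its own parameter, which is not an endpoint. The SAP foresees non-convergence and names AR(1) and then Fisher's test, which Protocol 6.7.2 already plans. The p-values are nominal, the study is described as hypothesis-generating (SAP 3.8), and the primary analysis is untouched. All of this stands, and it limits the point.

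It also rules out stronger readings that a reader might infer:

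- *The method cannot be estimated for the 84-letter endpoint.* The Week 24 contrast was finite in nearly every fit.
- *Empty cells are nearly certain.* The documents give no responder rates, and the chance ranges from 18.5% to 99.8% with the assumptions.
- *The unstructured correlation breaks down whenever a cell is empty.* That argument needs a visit with no responder in any arm. At assumed rates of 0.2% at Day 7 and 1% at Week 4, this has probability 0.998^150 = 74% and 0.99^150 = 22%.
- *All binary endpoints are affected.* BCVA ≥ 69 can be met at entry and had no empty cells. Leakage comes from angiography, scheduled after screening only at Weeks 12 and 24 up to Week 24. Fluid resolution was not examined.
- *Fisher's test discards strata and baseline.* The GEE as listed contains neither.

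What remains is that the visits are unstated, a run can report convergence with a meaningless cell so that no fallback is triggered, and the last fallback is discretionary and does not give the planned least squares means with 80% intervals.

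**Conclusion.** The point holds in a limited form. For BCVA of 84 letters or more, and for gains of 15 letters or more if early gains are modest, the planned GEE may meet cells that it cannot estimate, provided that early visits are in the model. The SAP implies this through its visit term but does not say so. The consequence is an unstable fit, especially with the identity link, and an unsettled choice of replacement. It is not the loss of the Week 24 comparison.

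The omission of strata and baseline BCVA does not depend on empty cells. It costs precision that is available from data already collected.

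The probabilities rest on assumed baseline, gains and early SDs; only the sample size, the entry limits and the Week 24 SD of 11 come from the documents. The fits used few data sets, no drop-out and one software package, so the convergence counts are indicative only. This should be changed before unmasking, but the primary result does not depend on it.

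**What to change.** In SAP 3.5.2, make the main analysis of each binary secondary endpoint a Week 24 logistic model with treatment, the BCVA and macular-laser strata, and continuous baseline BCVA. These are the covariates of the primary model; the anti-VEGF stratum is constant among treatment-naïve patients. Derive the odds ratio and the standardised risk difference, each with an 80% interval, from that one model. Drop the identity-link GEE.

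Prespecify a Firth penalty for sparse events, and name BCVA ≥ 84 letters as such a case. If the Week 24 rate were 11% (an assumption), 3 × 45 = 135 evaluable patients would give about 15 events for five covariate parameters. State how predicted risks are obtained under the penalty, because an uncorrected Firth fit pulls them towards one half.

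If the GEE is kept, the least that is needed is to list its visits, tie all estimates to Week 24, and make one sparse-cell method mandatory together with its 80% interval.

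The cost is SAP wording and routine programming. The small downside is that earlier visits no longer inform missing Week 24 values. At 10% drop-out that is about 5 of 50 per arm, and multiple imputation under the missing-at-random assumption of SAP 3.7 can cover it.

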1.2.3.2 Secondary Efficacy Outcome Measures

The secondary efficacy outcome measures include functional (BCVA) and anatomical (PD imaging) measures relevant to the mechanism of action of RO6867461 as follows:

BCVA:

- Proportion of patients gaining ≥ 15 letters from baseline BCVA at Week 24
- Proportion of patients with BCVA ≥ 69 letters (20/40 or better) at Week 24
- Proportion of patients with BCVA ≥ 84 letters (20/20 or better) at Week 24

Anatomic outcome measures by SD-OCT:

- Mean change from baseline in foveal center point thickness at Week 24
- Mean change from baseline in mean CST (1 mm diameter) at Week 24
- Proportion of patients with resolution of subretinal and intraretinal fluid at Week 24

Anatomic outcome measures by FFA:

- Proportion of patients with resolution of leakage at the macula at Week 24
- Change from baseline in the size of the foveal avascular zone at Week 24

Table 1 Description of Secondary Outcome Measures

Secondary EndPoint	Detailed Definition	Variable names used by central reading center
Foveal Center Point thickness (Central Foveal Thickness)	Thickness from Inner Limiting Membrane to the Retinal Pigment Epithelial at the horizontal slice closest to the center of the fovea	OCTCentralRetinalThickness1-3
mean CST	Mean thickness from Inner Limiting Membrane to the Retinal Pigment Epithelial over the 1 mm central subfield	OCTCentralSubfieldThickness1-3
intra-retinal fluid (IRF)	Presence of fluid within the retina	OCTIntraRetinalFluid
sub-retinal fluid SRF)	Presence of fluid between the retina and the retinal pigment epithelium	OCTSubretinalFluidThicknessNotPresent
Resolution of leakage at the macula	Resolution of fluorescein leakage at the macula	FAMaculaMLEakageArea1-3 or FAMaculaMLEakage
Size of the foveal avascular zone	Size of the foveal avascular zone (FAZ) by FFA	FAMaculaFAZArea1-3 FAMaculaFAZAreaB1-3

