The primary efficacy variable is the study eye BCVA change from baseline at Week 24. The primary efficacy analysis will be performed using a Linear Mixed Effects Model for Repeated Measurements (MMRM) model. The model will include the categorical covariates of treatment group, categorical visit, and visit by treatment group interaction term, randomization stratification factors, and a continuous covariate of baseline BCVA. An unstructured covariance will be used to account for within-patient correlation (General Linear Model), but another variance-covariance structure such as AR(1) + random patient effect may be selected in case of convergence issues. The primary statistical test will aim to test the null hypothesis:

H_0 : There is no difference between either of the RO6867461 arms (Arms B and C) and the control group (Arm A) for mean BCVA change from baseline at Week 24 in the treatment-naïve patient population vs.

H_A : Arm B or C is different from arm A.

The model-based estimate of the difference between each of the treatment groups (Arms B and C) and the control group (Arm A) at Week 24, together with 80% confidence interval and corresponding p-value will be reported as the primary

efficacy measures. The mean and 80% CI within each treatment group and for the difference between RO6867461 treatment groups (Arms B and C) and the control group (Arm A) at the other time points will also be reported. There will be no formal correction for multiple comparisons. Tests for arms B vs A and C vs A will be carried out at one-sided 10% alpha.

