3.5.3 Exploratory Efficacy Endpoints

Time to event endpoints will be tested with a two-sided stratified log rank test using the randomization stratification factors BCVA ETDRS letter score (64 letters or better vs. 63 letters or worse) and previous macular laser treatment as strata. Kaplan Meier curves will be displayed, and median time to event estimates will be computed.

Effect modification will be tested in the overall (treatment-naïve and previously treated combined) ITT population by adding a previous IVT anti-VEGF treatment status and a treatment arm by visit by previous IVT anti-VEGF treatment status interaction terms to the Linear model described in section 3.5.1. The treatment arm by visit by previous IVT anti-VEGF treatment status interaction term will be tested at a 10% significance level.

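### SAP 3.5.2 gives up efficiency: continuous anatomic secondaries are not adjusted for their own baseline, and the 69-letter GEE is adjusted for no baseline variable

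*SAP*

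**What the plan says.** **Continuous endpoints.** SAP 3.5.2: "For all key secondary endpoints measured on a continuous scale, a MMRM model described in section 3.5.1 will be used". The covariates that SAP 3.5.1 adds to treatment, visit and their interaction are "randomization stratification factors, and a continuous covariate of baseline BCVA". Nothing substitutes the baseline of the variable analysed. The continuous Week 24 secondaries in SAP 1.2.3.2 are changes in foveal center point thickness, in CST ("Mean change from baseline in mean CST (1 mm diameter) at Week 24") and in foveal avascular zone size. Protocol 6.7.2 likewise reuses the BCVA model.

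**Binary endpoints.** For the GEE, SAP 3.5.2 gives: "The model will include the categorical covariates of treatment group, visit, and visit by treatment group interaction term". One endpoint it serves is an absolute threshold, not a change: "Proportion of patients with BCVA ≥ 69 letters (20/40 or better) at Week 24". Protocol 4.2.1 admits eyes with 24 to 73 letters.

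**Strata.** SAP 2.1: "Randomization will be stratified for the three factors below". These are BCVA group (64 or better against 63 or worse), previous macular laser and previous IVT anti-VEGF. The third is constant among treatment-naïve patients. SAP 3.5.3 does use the first two: "Time to event endpoints will be tested with a two-sided stratified log rank test using the randomization stratification factors".

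**The concern.** A change score is usually correlated with its own starting value, so leaving that value out of the model leaves explainable variance in the residual. Baseline BCVA is only a partial stand-in for baseline retinal thickness or avascular zone size.

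For the 69-letter endpoint, the starting letter score is an obvious predictor: an eye entering at 70 needs no gain and an eye entering at 40 needs 29 letters. Allocation is also balanced on BCVA group and laser. An analysis that ignores those factors reports an SE that is too large and a test that is conservative.

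At stake is how much these secondary comparisons can show with about 45 evaluable patients per arm. The measurements needed are already scheduled: Protocol Appendix 1 has OCT and BCVA on Day 1 and angiography at screening.

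**Working it through.** **1. Evaluable number, from the plan's own figure.** SAP 1.3 gives 50 per arm, 10% dropout, SD 11, difference 5 letters and one-sided 10%.
- Evaluable: 50 × 0.9 = 45 per arm
- SE = 11 × √(2/45) = 2.319
- Power = Φ(5/2.319 − 1.2816) = Φ(0.875) = 0.809
- Minimum detectable difference = 1.2816 × 2.319 = 2.97

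The stated 80% and about 3 letters both reproduce. They concern the primary endpoint; only the 45 carries over.

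**2. Thickness endpoints.** Let ρ be the correlation of baseline with Week 24 thickness, and k the Week 24 SD divided by the baseline SD. The documents give neither, so both are assumptions. In units of baseline variance:
- change score without its own baseline: (1 − ρk)² + k²(1 − ρ²)
- with its own baseline: k²(1 − ρ²)
- if baseline BCVA is in the model and correlates c with baseline thickness, the first term of the first line is multiplied by (1 − c²)

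CI narrowing = 1 − √(adjusted variance / unadjusted variance). This treats Week 24 as a single-visit comparison.

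Example, k = 1, ρ = 0.5: 0.25 + 0.75 = 1 against 0.75, so the narrowing is 1 − √0.75 = 13.4%. The variance ratio of 1.33 makes 45 patients worth 45/1.33 = 34. If the own-baseline analysis had 80% power at one-sided 10%, the model as written would have 71%.

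| k | narrowing, ρ from 0.1 to 0.9 | same, with c = −0.5 |
|---|---|---|
| 0.75 | 25–37% | 21–32% |
| 0.85 | 15–32% | 12–27% |
| 1.0 | 2.5–26% | 1.9–21% |
| 1.1 | 0.02–22% | 0.02–18% |

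The gain vanishes when ρk = 1. The algebra also applies to foveal avascular zone size, for which no values were tried.

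**3. The 69-letter endpoint, by simulation.** Taken from the documents: 3 arms of 50, 10% dropout, stratified blocks, entry 24–73 letters, effect 5 letters, one-sided 10%. Assumed: block size 6, 20% previous laser, visits at Weeks 4–24 with residual correlation 0.7, and Week 24 change = 9 − slope × (baseline − 60) + effect. The model was a logit GEE with treatment by visit and unstructured correlation, comparing C with A. True SEs come from 10,000 trials per cell. Power comes from 5,000 trials per cell with the Kauermann-Carroll SE.

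| mean, SD, slope, residual SD | true SE: planned / + strata / + strata and BCVA | fall | power at nominal level, % | power at matched size, % |
|---|---|---|---|---|
| 61, 10, 0.25, 10.6 | 0.0966 / 0.0960 / 0.0927 | 4.0% | 60.9 to 65.7 | 62.0 to 64.6 |
| 61, 10, 0.4, 9 | 0.0955 / 0.0950 / 0.0923 | 3.4% | 71.9 to 76.2 | 74.1 to 76.3 |
| 58, 12, 0.25, 10.6 | 0.0972 / 0.0967 / 0.0918 | 5.6% | 59.2 to 65.4 | 60.4 to 63.5 |
| 63, 9, 0.1, 9 | 0.0916 / 0.0909 / 0.0867 | 5.3% | 65.8 to 72.2 | 69.2 to 71.4 |

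- Between 10% and 17% of patients meet the endpoint on Day 1.
- Strata alone lower the true SE by under 1%.
- The reported SE falls more, by 7–12%, because the planned SE is too large.
- Null rejection against 10%: planned 8.4–9.8%; adjusted with a plain robust SE 10.3–11.3%; adjusted and corrected 9.9–11.0% (Monte Carlo SE 0.3–0.4 points).
- Null coverage of the 80% CI: planned 81.3–82.8%; adjusted and corrected 78.6–80.2%.

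Single-visit simulations of the same input sets agree closely: true SE 2.6–6.3% lower, matched-size gains between 1.7 and 4.3 points, and planned-test rejection from 7.6%.

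**4. Dropout.** SAP 3.7 states missing at random for the primary analysis. With 10% dropout driven by baseline BCVA, the bias in the unadjusted 69-letter difference is essentially zero (at most 0.1 points) if the pattern is the same in both arms. It is about 1–2 points if one arm is selective and about 3–5 points if the arms are selective in opposite directions. The SE is √(2 × 0.45 × 0.55/45) = 0.105, or 10.5 points.

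**5. Other responder endpoints.** For 84 letters, adjustment lowers the true SE by 0–2% and raises null rejection by 1.0–1.9 points. For the 15-letter gain, the true SE moves between 0.4% higher and 1.7% lower. Fluid and leakage endpoints were not assessed.

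**The case against.** **It may be only wording.** SAP 3.5.2 can be read as naming a type of model, with baseline meaning that of the outcome analysed; SAP 3.4.2 defines baseline generically. This stands as a possibility. It makes the remedy a clarification, but the text as it is leaves the covariate unnamed.

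**Adjustment is already allowed.** SAP 3.5.2 adds: "Other statistical models and additional analyses may also be performed as appropriate". Protocol 6.7.2 lets baseline parameters enter the MMRM. But permission does not specify a covariate, and the baseline-parameter sentence in SAP 3.5.2 concerns only the primary endpoint. SAP 3.8 allows interim efficacy looks unmasked at group level, so a later choice of covariates would be harder to defend.

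**The 69-letter gain is too small, and the present test is safely conservative.** Much of this stands. The gain is a few power points on one secondary endpoint, one of three related responder endpoints would get a different model, and the adjusted test can run slightly above nominal. That part is therefore optional.

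**Stronger readings a reader might infer.** One is that the plan is biased or invalid. It is not: randomisation protects the contrasts, the unadjusted test errs towards too few rejections, and bias needs dropout that depends on baseline BCVA differently by arm. Another is that the 69-letter endpoint loses 8 to 13 power points. That comes from comparing tests of different size (7.3–8.8% against 9.8–11.4% null rejection), so part of it is recovered type I error. If change were unrelated to baseline with an SD of 8, below the planning SD of 11, the matched-size gain could reach about 5 points. The opposite reading, that the thickness loss must be trivial, is no better supported.

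**Conclusion.** The point holds as one of efficiency. As written, three continuous anatomic secondaries lack their own baseline, and the 69-letter GEE lacks baseline BCVA and the strata.

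The size rests on assumptions that the documents do not supply. Own-baseline adjustment narrows the thickness CI by anything from almost nothing to about a third over k from 0.85 to 1.1. For 69 letters, the true SE falls by about 3–6%, worth 2–4 power points at matched size, and adjustment removes the conservatism of a test that rejects about 8–10% against a nominal 10%.

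Severity is low: secondary p-values are nominal, SAP 3.8 calls the study hypothesis-generating, and the primary analysis already carries its own baseline and the strata.

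**What to change.** **Main change, SAP 3.5.2.** State that each continuous secondary MMRM includes the baseline of its own outcome plus the randomisation strata. This costs one clause and no new data.

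**Lower priority, 69 letters only.** Add continuous baseline BCVA, BCVA group and previous macular laser to the logit GEE. Report the standardised Week 24 risk difference with an 80% CI from a small-sample-corrected robust SE (for example Kauermann-Carroll). Keep the planned unadjusted GEE as supportive and as the fallback if the model does not converge. Leave the other binary endpoints as planned.

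This second change costs three covariates and a standardisation step. The adjusted odds ratio becomes conditional, so the standardised risk difference should lead. Null rejection may reach about 11% against 10% even with the corrected SE, and the SAP should say so.
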